***Statistical Methods******Analysis Population***

Safety analysis population will consist of all subjects who are dosed.

Efficacy analysis population will include the data from all subjects who are dosed and have efficacy data available.

***Extent of Exposure***

Descriptive statistics will be presented to summarize the volume of IP administered.

***Safety Analysis***

All patients receiving any dosage of IP will be included in the safety population on which safety analyses will be carried out. Summary tables, including change from pre-dose to post-dose where applicable, will be presented for the following safety endpoints:

- Adverse Events
- Clinical Laboratory Evaluations
- Vital Signs
- ECG abnormalities

All adverse events will be coded using MedDRA and summarized by system organ class and preferred term, by intensity and by causal relationship to the IP. Only those occurrences which occur from the start of IP administration through the follow-up period defined in the protocol will be tabulated in the Clinical Study Report as “adverse events”. Concomitant medications will be coded according to therapeutic area using the WHO drug reference list. Concomitant medications recorded between signing of informed consent and follow-up will be presented in data listings for all subjects dosed.

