### ***Objectives***

The objectives of this exploratory study are:

- to assess the ability of BR55 contrast-enhanced ultrasound (CEUS) to characterize pancreas lesions using transabdominal ultrasound (US) in subjects with suspected pancreatic ductal adenocarcinoma (PDAC) on the basis of a visual score (semi quantitative visual assessment of BR55 enhancement) using histopathology as the truth standard (TS);
- to expand the safety profile of BR55 in subjects with suspected pancreatic cancer.

Additional exploratory objectives of the study are:

- to correlate the signal intensity (SI) of the target lesion on BR55 CEUS with lesion type (malignant or benign) as determined by histopathology;
- to assess the correlation between SI of the target lesion on BR55 CEUS and VEGFR2 expression as determined by IHC;
- to assess the correlation between SI of the target lesion on BR55 CEUS and microvessel density (MVD) as determined by IHC.

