### ***Investigational Plan***

This is an exploratory, single center, open label, parallel-dose, and prospective study of BR55 CEUS for characterization of solid pancreatic lesions in subjects with suspected PDAC using transabdominal US. This study will be conducted in the US.

Approximately twenty-four (24) subjects with suspected PDAC and scheduled to undergo surgical resection or endoscopic ultrasound-guided fine needle biopsy (EUS-FNB) within 30 days (but not before 24 hours) after the transabdominal BR55 CEUS examination will be enrolled.

Subjects will be enrolled into 3 dose groups starting with the lowest dose group as follows:

- Dose group 0.03mL/kg
- Dose group 0.05mL/kg
- Dose group 0.08mL/kg

A maximum of 8 patients will be enrolled in each dose group according to the following methodology.

Enrollment into the next higher dose group will be based on the technical adequacy of the ultrasound acquisitions, as determined by a consensus medical review of images acquired in the first 4 subjects of the preceding dose group. Technical inadequacy of the ultrasound acquisitions will be determined in accordance with, but not limited to the following criteria:

- absent or insufficient contrast enhancement during the wash-in phase
- absent or insufficient contrast enhancement in subsequent image acquisitions (i.e. after the wash-in phase)
- lack of visualization of the target lesion in the post-contrast image acquisitions

Efficacy evaluations will be made on the US images that are acquired adequately. The Investigator will record the size, location and echogenicity of the lesion for UEUS. After BR55 is administered, the CEUS images will be evaluated for contrast enhancement using a semi-quantitative scale and a quantitative measurement of the SI in the target lesion vs. surrounding pancreatic tissue.

The final cancer diagnosis will be obtained for all subjects by histopathology.

Safety will be evaluated in this study by performing physical exams, collecting concomitant medications and the monitoring of adverse events, vital signs, electrocardiograms, laboratory tests and pulse oximetry.

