### Electrocardiograms

Acquire a 12-Lead ECG within 2 hours prior to and at approximately 30 min, 1 hour and 24 hours after BR55 administration. Attach a photocopy of the ECG report to the appropriate page of the Case Report Form.

ECG examinations will be performed locally and the ECG reports will be evaluated by a local cardiologist.

*Imaging Procedures*Ultrasound Equipment

The transabdominal UEUS and CEUS examinations will be performed with FDA-approved ultrasound equipment, commercially available for clinical applications. The BR55 CEUS evaluation of the pancreas should be performed with a contrast dedicated platform and equipped with a multi-frequency curved array transducer used for conventional transabdominal US examinations.

For standardization purposes, the same ultrasound system and transducer will be used for all subjects enrolled at the investigational site. Additionally, any technical interventions (including software release updates and periodic system maintenance) will be evaluated by the Sponsor in order to make sure the image quality is not affected.

A study dedicated preset will be installed on the selected ultrasound machine.

Ultrasound Image Acquisition

A detailed description of both the UEUS and BR55 CEUS acquisition protocols will be provided in a dedicated Imaging Manual.

The BR55 CEUS examination of the pancreas must be preceded by a standardized transabdominal UEUS examination of the pancreas to identify the focal target lesion. Oral fluid may be administered as needed to reduce shadowing gas in the stomach. Optimally, it should be possible to view the entire lesion within the field of view of the ultrasound transducer. UEUS will also serve to identify the optimal plane for imaging the target lesion after BR55 administration.

For the subsequent BR55 CEUS, to prevent microbubble destruction, the procedure should be performed in contrast mode using a low Mechanical Index.

Contrast inflow into the target lesion will be observed in the optimal imaging plane for approximately 60 seconds and using a low frame rate. Post-contrast images will be acquired at 2 minute time intervals, starting at 2 minutes and continue up to 30 minutes post BR55 administration, or until stationary enhancement in the lesion is no longer visible, whichever occurs first.

A copy of the DICOM images will be transferred to the Bracco Imaging Core Laboratory.

*Efficacy Evaluations*Unenhanced Ultrasound (UEUS) Assessment

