#### *Data Handling*

All data collected will be entered into the database and displayed in the subject data listings. In general, no imputation algorithms will be used to estimate missing safety and efficacy data, and tables will display counts of missing values.

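### The planned ECG summary covers abnormalities only, so a group-wide shift in an ECG interval that no reader calls abnormal would appear in no planned table

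*Combined protocol and SAP*

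**What the plan says.** Under Objectives, one of the two leading aims is "to expand the safety profile of BR55 in subjects with suspected pancreatic cancer".

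The Electrocardiograms section sets four time points: "Acquire a 12-Lead ECG within 2 hours prior to and at approximately 30 min, 1 hour and 24 hours after BR55 administration". Table B in the Study Schedule agrees. On recording, the section says "Attach a photocopy of the ECG report to the appropriate page of the Case Report Form". On reading, it says that "ECG reports will be evaluated by a local cardiologist". It names no interval and no rate correction, and it does not define an abnormality.

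In Statistical Methods, the Safety Analysis section states: "Summary tables, including change from pre-dose to post-dose where applicable, will be presented for the following safety endpoints". Four endpoints follow: adverse events, clinical laboratory evaluations, vital signs and "ECG abnormalities".

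The Data Handling section adds: "All data collected will be entered into the database and displayed in the subject data listings".

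**The concern.** An ECG interval is a continuous measurement. Each subject has a pre-dose value and three post-dose values, so change from pre-dose can be calculated at no extra burden to the subject. The plan's only ECG endpoint is a category, and an undefined one.

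A category of this kind picks up a subject whose tracing is judged abnormal. It is poorly suited to a modest shift shared by most of a dose group, because each tracing can be unremarkable on its own. In a study this small, where few abnormal readings can be expected, the average change is the more informative summary. Without it, the safety report could state how many abnormal ECGs were seen at each dose but not how the intervals moved.

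**Working it through.** **No plan figure to reproduce.** The Sample Size section says the number of subjects has no statistical basis, and the documents give no figure for ECG intervals.

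**Sections side by side**

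- *Vital Signs* names systolic pressure, diastolic pressure and heart rate, each with its unit. *Electrocardiograms* names no parameter.
- *Safety Analysis* attaches the change-from-pre-dose clause to all four listed endpoints. For ECG the listed endpoint is abnormalities, so the clause most naturally gives a change in abnormality status. It does not bring in intervals.
- *Data Handling* promises listings of the data collected. A listing is not a summary, and the Electrocardiograms section does not say that interval values are entered as data.

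Read together, these sections do not lead to a table of interval change.

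**Number of ECGs.** 4 per subject × 24 subjects = 96. For a full dose group, 4 × 8 = 32.

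**Precision if intervals were summarised.** The 95% half-width for a mean change is t(0.975, n−1) × SD / √n. The group size comes from the Investigational Plan ("A maximum of 8 patients will be enrolled in each dose group") and the total from the planned 24. The SD of change is an assumption, because the documents give none.

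| n | t/√n | SD 8 ms | SD 10 ms | SD 15 ms | SD 20 ms |
|---|---|---|---|---|---|
| 8 (one full dose group) | 0.836 | ±6.7 | ±8.4 | ±12.5 | ±16.7 |
| 24 (pooled) | 0.422 | ±3.4 | ±4.2 | ±6.3 | ±8.4 |

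The Administration section lets enrolment move to the next dose when the first 4 subjects' images are technically inadequate. For n=4 the multiplier is 3.182/2 = 1.591, which gives about ±24 to ±32 ms at an SD of 15 to 20 ms.

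**How easily a count can miss a shift.** This is an illustration on assumed values only: pre-dose QTc normally distributed with mean 400 to 420 ms and SD 15 to 20 ms, and a reader who calls anything above 450 ms abnormal. None of these values is in the documents. Let every subject rise by 10 ms, and let p be the share then above the limit. The chance that none of 8 crosses it at one time point is (1−p)^8.

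- Mean 400, SD 15: p = 0.4%, chance of none 97% (99.7% without the rise).
- Mean 420, SD 20: p = 15.9%, chance of none 25% (57.5% without the rise).

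Across this range, a dose group with a real 10 ms shift shows no abnormal reading between 25% and 97% of the time.

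**The case against.** Several points on the other side have force.

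- **The change clause covers all four endpoints.** A reader might infer that laboratory values and vital signs are promised as values with change while ECG is deliberately denied this. The text draws no such line, and a shift table of abnormalities is a fair reading of what is already planned. The clause still names no interval, so the gap remains.
- **The case report form is not available.** A reader might infer that interval values are not captured at all. The documents do not show that. They say a photocopy is attached, not that nothing else is recorded, and further fields may exist. If they do, Data Handling would put the values in listings, but the summary endpoint would still need changing.
- **An abnormality is not defined.** It could include an abnormal change from pre-dose. So it cannot be said that a particular rise, from one stated value to another, would be counted as normal; that depends on a cut-off the plan does not give.
- **The cardiac exclusions.** A reader might take these as evidence of a known cardiac concern with BR55. The exclusion criteria give no reason, so they do not support that.
- **Clinical reporting.** A cardiologist evaluates each report, and untoward events are recorded through 24 hours. A change judged important in one subject therefore has a route into the report. A small average shift does not.
- **Limited gain.** With at most 8 subjects per dose, one pre-dose ECG and no control arm, a mean change could not be separated from time-of-day or procedural effects. This stands, and it limits what the new table can claim.

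**Conclusion.** The point holds as a gap in the planned summaries: as supplied, the plan leads to no table of ECG interval change, although the ECGs are already scheduled and safety is a stated objective. It is a worthwhile, low-cost improvement and does not undermine the study.

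The gain is descriptive. At an assumed SD of change of 15 to 20 ms, the mean change would be known to about ±6 to 8 ms pooled and ±13 to 17 ms in a full dose group. A smaller SD would tighten both; a group stopped at 4 subjects would do much worse. The pooled figure needs all 24 subjects with evaluable ECGs and averages over three doses.

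A reader might infer that the revised table would establish or exclude a dose-related ECG effect. It would not, for the reasons of size and design given above. Nor do the documents support saying that interval data are being thrown away, only that the plan does not provide for summarising them.

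**What to change.** In Statistical Methods, Safety Analysis, replace "ECG abnormalities" with wording such as: *ECG: heart rate, PR, QRS, QT and QTc (correction formula pre-specified), value and change from pre-dose at 30 min, 1 h and 24 h, by dose group and pooled, with 95% CI; plus a pre-dose to post-dose shift table of abnormalities.* State what counts as an abnormality for that table.

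In the Electrocardiograms section, require the interval values to be entered on the case report form, if they are not already, in addition to attaching the report. State in the analysis text that the intervals are descriptive and uncontrolled.

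The cost is data entry for up to about 96 ECGs and one more table. No visit, procedure, dose or clinical rule changes.

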***Efficacy Analysis*****General**

Efficacy analysis will include the data from all evaluable subjects who are dosed and have efficacy data available. The results will be presented for each dose group, if applicable. Except as noted, the statistical tests will be two-sided at the 0.05 level of significance with 95% confidence limit.

**Characterization of Pancreatic Lesions – by BR55 CEUS Visual Score Using  
Histopathology as the Truth Standard (TS)**

The objective of this study is to determine the ability of BR55 CEUS to characterize pancreatic lesions in subjects with suspected PDAC on the basis of a visual score (semi quantitative visual assessment of BR55 enhancement) using histopathology as the TS.

CEUS images of the pancreas will be assessed by the investigator as 3-point scale for contrast enhancement of BR55 (none, weak enhancement, and strong enhancement), while TS assessment result will be classified as malignant if cancer is found or as benign if no cancer is found. Frequency tables will be provided for BR55 enhancement scores by TS assessment results (malignant and benign).

#### Signal Intensity (SI) of the Target Lesion on B55 CEUS vs. TS

SI will be defined as the quantitative assessment of BR55 enhancement of the target lesion on BR55 CEUS.

Summary statistics will be provided for SI by TS (malignant and benign). If data are available, a t-test or non-parametric test will be performed to test for a difference in mean SI on BR55 CEUS between the malignant and benign lesions per TS.

Furthermore, SI on BR55 CEUS will be categorized as no signal, low signal, and high signal, cross tabulation of the 3 SI categories versus TS will be presented.

In addition, exploratory analyses, such as ROC analysis of SI on BR55 CEUS in predicting presence of a malignant lesion as determined by TS and logistic regression will be performed if data is available and deemed as needed for this exploratory study.

#### Correlation between SI of the target lesion on BR55 CEUS and VEGFR2 expression as determined by IHC

To investigate relationship between SI of the target lesion on BR55 CEUS and VEGFR2 expression level, the Spearman correlation coefficient between the SI and VEGFR2 will be estimated.

#### Correlation between SI of the target lesion on BR55 CEUS vs. microvessel density (MVD)

To investigate the relationship between SI of the target lesion on BR55 CEUS and MVD, The Spearman correlation coefficient between SI and MVD will be estimated.

#### *Sample Size*

This is an exploratory study. The sample size determination is not based on the statistical considerations and assumptions. Approximately 24 subjects will be prospectively enrolled into three groups to receive BR55 at 0.03 mg/kg, 0.05 mg/kg and 0.08 mg/kg dose levels.

#### *Data Handling*

All data collected will be entered into the database and displayed in the subject data listings. In general, no imputation algorithms will be used to estimate missing safety and efficacy data, and tables will display counts of missing values.

**BR55**

**Final Version**  
**10 April 2019**

---

*Interim Analyses*

No interim analysis is planned.
